#### **6.2.7. Liver fibrosis endpoint**

Liver fibrosis will be assessed using non-invasive FibroScan in all study subjects, and by formal liver biopsy in a subset of study subjects.

To assess liver fibrosis changes non-invasively a liver stiffness measure (LSM) will be obtained for all patients by transient elastography using FibroScan (EchoSens) at times outlined in Table 1.

. The LSM result will be expressed as a median value of the total measurements in kiloPascal (kPa). Only subject examinations with at least 10 validated measurements, a success rate of at least 60%, and an interquartile range (IQR) of all validated measurements of less than 30% will be considered a reliable LSM measure. Mean changes of LSM at Week 48, Week 96, Week 144, Week 192 and Week 240 will be reported.

To evaluate the proportion of subjects who experience an improvement in histology at Week 216 a subset of study subjects (approximately 100 subjects) will undergo liver biopsies at times outlined in Table 1.

A single central pathologist will evaluate all baseline and final biopsy slides in a paired fashion and blinded to timing of biopsy. The baseline and end of treatment biopsies will be read at the same time. (See Appendix 3)

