6. STATISTICAL CONSIDERATIONS

6.1 General rule

All analysis will be conducted using SAS® Version 9.2 or higher (SAS Institute, Cary, NC). For continuous variables, descriptive statistics will be presented as the mean, standard deviation, minimum, median, maximum, and the number of observations, unless otherwise specified. For categorical variables, the number and percentage for each of the categories will be presented. Counts that are zero will be displayed as “0”. Unless otherwise specified, the denominator for all percentages will be based on the number of subjects in the analysis set of that treatment group. Baseline is defined as the last assessment before administration of the study drug.

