7.4.3 Exploratory analysis

Incidence of TDF resistance substitutions such as mutation change, drug resistance test results will be summarized in patients with unsatisfied virological response, viral breakthrough, or discontinued treatment with HBV DNA ≥ 20 IU/mL.

Univariate and multivariate analysis by logistic regression model will be performed to identify baseline or on-treatment risk factors associated with HCC and disease progression, if applicable. The factors will include gender, age, genotype, baseline HBV DNA category (≥ 2000 or < 2000, IU/mL), baseline HBeAg sero-status, baseline ALT value, baseline LSM value, Week 24 treatment response, Week 48 treatment response. Treatment response is defined as serum HBV DNA < 20 IU/mL. Multivariate analysis will include sex, age and the factors with P ≤ 0.20 in univariate analysis.

Time to HCC/disease progression will be analyzed by cox model. Univariate will be conducted to include all above factors and the selection of multivariate analysis will follow the same rule.

Impact of HBV DNA and virologic response on change of LSM will be summarized by shift table

of descriptive statistics as the mean, standard deviation, minimum, median, maximum, and the number of observations.

The mean changes and percent of the changes of liver stiffness measurement in each visit will be summarized by descriptive statistics as the mean, standard deviation, minimum, median, maximum, and the number of observations for patients with advanced fibrosis and compensated cirrhosis. Compensated cirrhosis is defined as $LSM \geq 12.0$ Kpa ($ALT \leq ULN$) or $LSM \geq 17.5$ Kpa ($ALT > ULN$); advanced fibrosis is defined as 9.0 Kpa $\leq LSM < 12.0$ Kpa ($ALT \leq ULN$) or 12.4 Kpa $\leq LSM < 17.5$ Kpa ($ALT > ULN$).

Time to improvement of fibrosis will be analyzed by cox regression. Improvement of fibrosis is defined as at least 30% decrease of LSM compared with baseline. Univariate analysis will include gender, age, genotype, baseline HBV DNA category (≥ 2000 or < 2000 , IU/mL), baseline HBeAg sero-status, baseline ALT value, Week 24 treatment response, Week 48 treatment response. Treatment response is defined as serum HBV DNA < 20 IU/mL. Multivariate analysis will include sex, age and the factors with $P \leq 0.20$ in univariate analysis.

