The relationship between baseline variables or on-treatment variables and improvement of fibrosis will be analysis by univariate and multivariate logistic model. Univariate analysis will include gender, age, BMI category (< 25 or ≥ 25 kg/m²), baseline HBV DNA (≥ 2000 or < 2000 , IU/mL), baseline HBeAg sero-status, baseline ALT value, baseline LSM value, baseline total bilirubin, HBeAg loss at Week 24, treatment response at Week 24 and Week 48, ALT normalized or not at Week 24 and Week 48, change from baseline of LSM at Week 12 and Week 24, change from baseline of GGT at Week 24. Multivariate analysis will include sex, age and the factors with $P \leq 0.20$ in univariate analysis.

Proportion of LSM improvement will be summarized at Week48, Week96, Week144, Week192 and Week240 for patients with baseline LSM result in following groups: LSM improved (LSM decreased from baseline $\geq 30\%$), LSM stable (LSM decreased from baseline $< 30\%$ or no change from baseline), and LSM deteriorate (LSM increase from baseline).

Proportion of fibrosis stage improvement will be summarized at Week 48, Week 96, Week 144, Week 192 and Week 240 for patients of fibrosis stage measured by fibrosis improved from baseline, ≥ 2 stage fibrosis stage improved from baseline, ≥ 1 stage fibrosis stage, no change from baseline, fibrosis stage increase from baseline.

Analyses of correlation coefficients between LSM and ALT level will be analyzed by Pearson correlation coefficients and P-value during every 48 weeks by patients with ALT normal at baseline, patients with abnormal at baseline and overall.

Correlation coefficients between variables change at Week 12 and 24 and LSM change at Week 240 will be analyzed by correlation coefficients and P-value. The change from baseline of Gamma-Glutamyltransferase (GGT), Total Bilirubin (TBIL), Albumin (ALB), International Normalized Ratio (INR) and LSM will be included in the analysis of correlation coefficients at Week 12, platelets (PLT), GPR, APRI, FIB-4 and all the variables included at Week 12 will be included in the analysis of correlation coefficients at Week 24.

A 5-years predicted HCC risks by REACH-B model (see Section 8.5) and observed HCC risks (cumulative incidence of HCC) at Week 240 will be presented in table. Decline in LSM from baseline to Week 240 by visit will be analyzed by a line plot.

In addition, a listing of HBV DNA result will be provided for the following patients:

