8. APPENDIX

8.1 Appendix 1: Description of Inclusion/Exclusion Criteria

Seq No	Type	Description
1	Inclusion	Age 18-60 years(inclusive)
2	Inclusion	Presence of HBsAg in serum at screening and for at least 6 months before screening assessment
3	Inclusion	Serum HBV DNA ≥ 2000 IU/mL if HBeAg positive at screening (with or without ALT elevation); or serum HBV DNA ≥ 200 IU/mL if HBeAg negative at screening (with or without ALT elevation)
4	Inclusion	
Pathologically or clinically diagnosed as advanced fibrosis or compensated cirrhosis defined as one of following(a or b) :
 
a. Liver biopsy showing advanced fibrosis or cirrhosis (Ishak score ≥ 4 or Fibrosis stage $\geq S3$ by Scheuer Score, or within the previous 6 months before baseline and provided that no treatment likely to improve liver histology has been taken since). The slides must be available for review by an independent histopathologist.
 
b. Clinical diagnosis: liver stiffness measure (LSM) > 12.4 kpa (ALT $> ULN$) or LSM > 9.0 kpa (ALT $\leq ULN$), plus one of the following:
 
 • Endoscopy-proven gastroesophageal or gastric varices, non-cirrhotic portal hypertension excluded; • Abdominal ultrasound or CT found changes indicating cirrhosis, irregular liver surface or nodularity, with/without splenomegaly(depth of spleen > 4.0 cm or spleen length > 13 cm); • Blood platelets $< 100 \times 10^9/L$ (and other causes of thrombocytopenia excluded);
5	Inclusion	
Ability to give written informed consent
 
A female is eligible to enter and participate in this study if she is of:
 
a. Non-childbearing potential (i.e., physiologically incapable of becoming pregnant, including any female who is post-menopausal), or
 
b. Child-bearing potential, has a negative urine pregnancy test at screening, and agrees to one of the following methods for avoidance of pregnancy during the period of the study and until 30 days after last dose of study medication:

6	Inclusion	
 • Oral contraceptive, either combined or progestogen alone. • Injectable progestogen. • Implants of levonorgestrel. • Oestrogenic vaginal ring. • Percutaneous contraceptive patches. • Intrauterine device (IUD) or intrauterine system (IUS) showing that the

Seq No	Type	Description

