Table	4.7.3	The Proportion of Subjects Achieving HBsAg Loss and HBsAg Seroconversion at Week 48, 96, 144, 192 and 240 for Subjects with Negative HBeAg at Baseline - mITT
Table	4.8.1	Change from Baseline for the log ₁₀ IU/mL in Serum HBV DNA by Visit - mITT
Table	4.9.1	Incidence of Subjects Who Experience Viral Breakthrough by Visit - mITT
Table	4.9.3	Incidence of Subjects With Unsatisfied Response by Visit - mITT
Table	4.10.1	The Proportion of Subjects with Histological Improvement - mITT
Table	4.11.1	The Proportion of Subjects with Cirrhosis Reversal - mITT

Table	4.12.1	The Mean Changes of Liver Stiffness Measurement by Visit - mITT
Table	4.12.3.1.1	Shift from Baseline in Fibrosis Stage for Patients with Baseline ALT > ULN - mITT
Table	4.12.3.2.1	Shift from Baseline in Fibrosis Stage for Patients with Baseline ALT ≤ ULN - mITT
Table	4.12.3.3	Shift from Baseline in Fibrosis Stage - mITT
Table	4.13.1	Incidence of TDF Resistance Substitutions - mITT
Table	4.14.1	The Relationship Between Baseline Variables or On-treatment Variables and Newly Diagnosed Hepatocellular Carcinoma (HCC) - mITT
Table	4.14.3	The Relationship Between Baseline Variables or On-treatment Variables and Disease Progression - mITT
Table	4.17.1	Cox Regression Analysis for Time to Newly Diagnosed Hepatocellular Carcinoma (HCC) - mITT
Table	4.17.3	Cox Regression Analysis for Time to Disease Progression - mITT
Table	4.18.1	Impact of HBV DNA and Virologic Response on Change of LSM - mITT
Table	4.18.3	The Mean Changes of Liver Stiffness Measurement by Visit for Patients with Advanced Fibrosis and Compensated Cirrhosis - mITT
Table	4.18.3.1	The % Changes of Liver Stiffness from baseline by Visit for Patients with Advanced Fibrosis and Compensated Cirrhosis - mITT
Table	4.19.7	Cox Regression Analysis for Time to Improvement of Fibrosis - mITT
Table	4.20.3	The Relationship Between Baseline Variables or On-treatment Variables and Improvement of Fibrosis - mITT
Table	4.21.1	Proportion of LSM Improvement - mITT
Table	4.21.3	Proportion of LSM Stage Improvement - mITT
Table	4.22.1	Analyses of correlation coefficients between LSM and ALT level - mITT
Table	4.23.1	Analyses of correlation coefficients between Variables Change at Week 12 and 24 and LSM Change at Week240 - mITT
Table	4.24.1	Predicted and Observed Risk of HCC at Week240 - mITT
Table	5.3.4	Mean values in Non-invasive fibrosis - SA
Table	5.1.1	Overall Summary of Adverse Events - SA

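### The exploratory LSM response table counts any rise as deterioration but asks for a 30% fall before it counts improvement, so it overstates worsening of stiffness

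*SAP*

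**What the plan says.** SAP section 7.4.3 defines three groups, summarised at Weeks 48, 96, 144, 192 and 240 in subjects with a baseline LSM:

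- The first group, "LSM improved (LSM decreased from baseline", requires a fall of 30% or more.
- The stable group takes falls smaller than 30%, and the text then continues "or no change from baseline), and LSM deteriorate (LSM increase from baseline".
- The last group, "LSM deteriorate (LSM increase from baseline", has no minimum rise, tolerance band or confirmation, and no other section of either document adds one.

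The result is Table 4.21.1, "Proportion of LSM Improvement - mITT". SAP section 5.3 lists the endpoint as exploratory. The 30% limit is also used for the fibrosis-improvement models: "Improvement of fibrosis is defined as at least 30% decrease of LSM compared with baseline".

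On measurement, Protocol section 6.2.7 reports LSM as the median of at least 10 valid measurements and states that "an interquartile range (IQR) of all validated measurements of less than 30% will be considered a reliable LSM measure". Neither document gives a between-visit repeatability figure.

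**The concern.** The rule treats a small fall as noise and an equally small rise as worsening. A subject going from 14.0 to 10.0 kPa (-28.6%) is stable, while one going from 14.0 to 14.1 kPa (+0.7%) has deteriorated.

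Elsewhere the SAP asks worsening to reach a set size, be confirmed, or both. Examples are a Child-Pugh rise of 2 or more points, creatinine clearance at or below 50 mL/minute on two occasions, and a 1 log10 rise in HBV DNA (SAP sections 5.1 and 5.2).

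A reader of a single-arm study will take the deteriorated row as the share of subjects whose stiffness worsened on TDF. If much of that row is reading error, the table misleads.

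**Working it through.** **No figure to reproduce.** The plan states no expected proportion for any LSM group.

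**Inputs from the documents.** The group limits are those of SAP section 7.4.3. SAP section 6.1 says "Baseline is defined as the last assessment before administration of the study drug", and Protocol Table 1 schedules Fibroscan at both screening and baseline. SAP section 6.2 falls back on the screening value if the baseline value is missing. The clinical entry route applies an LSM threshold: "Clinical diagnosis: liver stiffness measure (LSM) > 12.4 kpa" when ALT is above ULN, and 9.0 kPa otherwise.

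**Assumptions, not in the documents.** Each reading has independent log-normal error with the same CV at both visits. The CV is taken as 10-25%, with 5% added as a low extreme in the simulation.

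**Step 1: no true change.** With independent, identically distributed errors, P(follow-up > baseline) = (1 - P(tie))/2. This is one half less ties, whatever the CV. Simulation with values rounded to 0.1 kPa and true LSM of 10, 15 and 20 kPa gave 47.2% to 49.7% across CV 5-25%.

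**Step 2: closed form, ignoring rounding.** The log ratio of the two readings has SD = √2 × √ln(1 + CV²). With no true change:

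- P(fall ≥ 30%) = Φ(ln 0.7 / SD)
- P(rise ≥ 30%) = Φ(-ln 1.3 / SD)
- P(rise ≥ 43%) = Φ(-ln(1/0.7) / SD), which equals P(fall ≥ 30%)

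With a true fall of 10%, P(any rise) = Φ(ln 0.9 / SD).

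| CV | SD | Fall ≥ 30% | Any rise | Rise ≥ 30% | Rise ≥ 43% | Any rise, true 10% fall |
|---|---|---|---|---|---|---|
| 10% | 0.141 | 0.6% | 50% | 3.1% | 0.6% | 22.8% |
| 15% | 0.211 | 4.5% | 50% | 10.7% | 4.5% | 30.9% |
| 20% | 0.280 | 10.1% | 50% | 17.4% | 10.1% | 35.3% |
| 25% | 0.348 | 15.3% | 50% | 22.6% | 15.3% | 38.1% |

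For example, at CV 20%, ln 0.7 / 0.280 = -0.357 / 0.280 = -1.27, and Φ(-1.27) = 10%.

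**Step 3: larger true falls.** Over CV 10-25%, the deteriorated share is 6-26% with a true 20% fall and 1-15% with a true 30% fall.

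**Step 4: entry selection.** Simulation applied the two LSM entry thresholds to an assumed log-normal distribution of true LSM (medians 15 and 12 kPa, log SD 0.45), again with no true change. With a separate pre-dose reading as baseline, the deteriorated share is 49.0-49.6%. If the entry reading is itself the baseline, regression to the mean lowers it to 41.7-46.2% (CV 10-25%).

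**Step 5: are small rises within reading error?** Suppose the IQR limit is relative to the median and the measurements are independent and normal. An IQR of 30% then implies an SD of 30/1.349 = 22% per measurement. The median of 10 has an error of about 1.253 × 22/√10 = 9%. This is the most the reliability rule permits under those assumptions, and it excludes any variation between visits. It shows only that a rise of a few percent need not be a real change.

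**The case against.** Several stronger conclusions are tempting, and the documents do not support them.

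- **That half of the cohort would be reported as worse.** The half applies only to subjects with no true change. The protocol's rationale (section 1.2) cites halting or regression of fibrosis in 96% of patients on long-term TDF. If stiffness falls, the share drops as Step 3 shows. A subject whose measured value is identical at both visits is classed as stable.
- **That this is the main categorical fibrosis result.** It is exploratory. The secondary categorical result is the fibrosis-stage change (SAP sections 5.2 and 7.4.2.3), where a rise counts only if it crosses a stage cut-off.
- **That the table is biased against treatment, or hides how many subjects progressed.** There is one arm and no planned comparison (Protocol section 8.3.3). Disease progression is a primary endpoint whose definition does not use LSM.
- **That the 30% IQR rule measures between-visit error.** It concerns spread within one examination, so the CV range remains an assumption.

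It can also be argued that counting every rise is a cautious choice in an uncontrolled study, and that the size of any rise can be seen in Tables 4.12.1 and 4.18.3.1 and Listing 4.4.

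These points limit the consequence and stand to that extent. They do not justify the label. A row called deteriorated that collects about half of truly unchanged subjects misdescribes them, and this part of the argument does not depend on the assumed CV.

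**Conclusion.** The point holds as a minor one. As written, the rule labels about half of truly unchanged subjects as deteriorated: 47-50% with a separate pre-dose baseline, or about 42-46% if the entry reading is the baseline. Against this, 1-15% are labelled improved. With a true 10% fall, 23-38% are still labelled deteriorated.

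The one-half result rests on independent errors with the same distribution at both visits. The other figures rest also on log-normal error and the assumed CV of 10-25%, and the 42-46% additionally on an assumed distribution of true LSM.

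The effect is confined to the split between stable and deteriorated in Table 4.21.1, which overstates worsening of stiffness. The improved proportion, the fibrosis-improvement models, the fibrosis-stage shifts, the mean and percent change tables and both primary endpoints do not use that split.

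**What to change.** In SAP section 7.4.3 and Table 4.21.1:

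1. Pre-specify a minimum rise for deterioration that matches the 30% improvement limit, and state the scale. On the percent scale this is a rise of at least 30%. On the ratio scale the true mirror is 1/0.7, a rise of at least 43%: 20.0 to 14.0 kPa is a 30% fall, and 14.0 to 20.0 kPa is a 43% rise. The choice matters. At CV 20% with no true change, false deterioration is 17% with the first limit and 10% with the second, against 10% false improvement.
2. Define stable as everything between the two limits.
3. Keep the present third group as a separate row labelled as any increase.

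The cost is a short wording change and a small programming change, with no new data. The downside is that some moderate rises move to stable, including some that cross a stage cut-off. For example, 14.0 to 18.0 kPa (+28.6%) with baseline ALT above ULN crosses the SAP's 17.5 kPa boundary between F3 and F4. Such subjects stay visible in the any-increase row, in the stage-shift tables (4.12.3.1.1, 4.12.3.2.1 and 4.12.3.3) and in Table 4.21.3.

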7.5 Safety analysis

Safety endpoints include adverse events, vital signs, laboratory assessments, physical examination,

and B-ultrasound. The analysis will be conducted in SA population.

7.5.1 Adverse events

AEs will be classified into standardized medical terminology from the verbatim description (investigator term) using the Medical Dictionary for Regulatory Activities (MedDRA). Verbatim description and MedDRA level terms, including the system organ class, preferred term, and lower level term, for all AEs will be presented in the data listings. In table summaries, the denominator for percentages will be the number of subjects in the treatment group within the safety analysis population. AEs are coded according to (MedDRA) version 17.0.

TEAE is defined as AE occurred on or after the first dose date of study drug. TEAEs will be presented by system organ class and preferred term. The subject level incidence is only one occurrence of a preferred term/system organ class per subject. If a subject reports multiple AEs under the same preferred term, then the count of subject level incidences for that preferred term will only be incremented by one. If a subject reports multiple AEs under the same system organ class, then the count of subject level incidences for that system organ class will also only be incremented by one. System organ classes will be presented in descending order of total frequency of subject level occurrences. Within each system organ class, preferred terms are presented in the same descending order of total frequency of subject level occurrences.

An overall summary table of AE will be provided, including summaries of all AEs, all TEAEs, all treatment related TEAEs, all serious TEAEs, all treatment related serious TEAEs, all TEAEs leading to permanent discontinuation of study drug, all TEAEs leading to permanent discontinuation from the study, and all TEAEs that caused a change in dose or temporary interruption of study drug. Listings will be provided correspondingly.

All TEAEs and all serious TEAEs will be summarized by SOC and PT, and by intensity. All TEAEs will also be summarized by relationship to study drug.

7.5.2 Vital sign

Vital signs including systolic blood pressure (mmHg), diastolic blood pressure (mmHg), pulse (beats/minute), respiratory rate (breaths/minute), body temperature (°C) and weight (kg) will be descriptively summarized by visit. Changes from baseline to each individual post-baseline visit will also be presented.

A listing of vital signs will be provided.

7.5.3 Laboratory assessments

Summary tables of hematology and blood chemistry by visit will be provided including the changes from baseline for each post-baseline visits. Descriptive statistics will be used for quantitative variables. For qualitative variables, the number and percentage for each parameter will be presented.

Treatment-emergent grade 3 or grade 4 laboratory abnormalities are defined as values that increase at least one grade from baseline and get Grade 3 (severe) or 4 (potentially life threatening) at any post-baseline value (as defined in Appendix 3). If the relevant baseline laboratory data are missing, then the screening laboratory result will be used; if it is missing then any Grade 3 or 4 post-baseline values are considered treatment emergent.

The following summaries (number and percentage of subjects) of treatment-emergent laboratory abnormalities will be provided:

- Treatment-emergent Grade 3 or Grade 4 laboratory abnormalities
- Incidence of on-treatment hepatitis exacerbation defined as bilirubin ≥ 2 times ULN or albumin ≤ 3 g/dL or ALT ≥ 20 times ULN (and ≥ 2 times baseline)
- Confirmed (defined as two consecutive visits) serum creatinine ≥ 0.5 mg/dL above baseline
- Confirmed (defined as two consecutive visits) serum phosphate < 2 mg/dL
- Calculated creatinine clearance < 50 mL/min

Mean estimated glomerular filtration rate (eGFR) over time by baseline eGFR, mean creatinine

clearance rate (Ccr) over time by baseline Ccr, mean serum phosphorus over time will be analyzed by line plots, respectively.

Change of average LSM/ALT by visit, change of average LSM by visit, change of median of LSM by visit, change of average GPR/APRI/FIB-4 by visit, change of median of GPR/APRI/FIB-4 by visit, change of fibrosis stage by visit will be analyzed by line plots, respectively.

In addition, listings of hematology, blood chemistry, blood coagulation, urinalysis, pregnancy test, and alpha fetoprotein (AFP) will be provided.

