## 6. STUDY ASSESSMENTS AND PROCEDURES

**Table 1 Time and Events Table**

Procedures	Screening  ( ≤ 4 weeks prior to dosing)  Visit 1	Baseline (Day 0) Visit 2	First Year (Week)  Visit 3~6				Second year (Week)  Visit 7~10				third Year to Fourth year (Week)  Visit 11~18				Last Year (Week)  Visit 19-22				Withdraw  (Week off treatment)
			12 ±6 d	24 ±6 d	36 ±6 d	48 ±6 d	60 ±6 d	72 ±6 d	84 ±6 d	96 ±6 d	108 ±6d	120 ±6d	132 ±6d	144 ±6d	204 ±6d	216 ±6d	228 ±6d	240 ±6d	
			156 ±6d	168 ±6d	180 ±6d	192 ±6d													
Written informed consent	√																		
Subject demography 	√																		
Medical history	√ 	√ 																	
Inclusion/exclusion criteria	√																		
Concomitant medication 		√	√	√	√	√	√	√	√	√	√	√	√	√	√	√	√	√	√
Physical examination 	√	√	√	√	√	√	√	√	√	√	√	√	√	√	√	√	√	√	√
Vital signs 	√	√	√	√	√	√	√	√	√	√	√	√	√	√	√	√	√	√	√
Adverse events		√	√	√	√	√	√	√	√	√	√	√	√	√	√	√	√	√	√
Serious adverse events		√	√	√	√	√	√	√	√	√	√	√	√	√	√	√	√	√	√
Laboratory assessments																			
Haematology	√	√		√		√		√		√		√		√		√		√	√
Chemistry(Liver & Renal function, electrolyte(phosphate and calcium inclusive))	√	√	√	√	√	√	√	√	√	√	√	√	√	√	√	√	√	√	√
Pregnancy test 	√	√	√	√	√	√	√	√	√	√	√	√	√	√	√	√	√	√	√
HAV/HCV/HDV/HEV/HIV / ANA	√																		
B-ultrasound 	√	√	√	√	√	√	√	√	√	√	√	√	√	√	√	√	√	√	√

Fibroscan	√	√	√	√	√	√	√	√	√	√	√	√	√	√	√	√	√	√	√
AFP	√	√	√	√	√	√	√	√	√	√	√	√	√	√	√	√	√	√	√
Urinalysis 	√	√	√	√	√	√	√	√	√	√	√	√	√	√	√	√	√	√	√
Prothrombin time and INR	√	√	√	√	√	√	√	√	√	√	√	√	√	√	√	√	√	√	√
HBV DNA 	√	√	√	√	√	√	√	√	√	√	√	√	√	√	√	√	√	√	√
HBeAg/Anti-HBe	√	√	√	√	√	√	√	√	√	√	√	√	√	√	√	√	√	√	√
HBsAg/Anti-HBs	√	√	√	√	√	√	√	√	√	√	√	√	√	√	√	√	√	√	√
Genotyping 		√																	
Genotypic analysis 							√	√	√	√		√		√		√		√	√
Investigational product																			
Study drug dispensed and reconciliation of drug supply 		√	√	√	√	√	√	√	√	√	√	√	√	√	√	√	√	√	√
Liver biopsy	√															√			
Serum and plasma storage	√	√	√	√	√	√	√	√	√	√	√	√	√	√	√	√	√	√	√

- 1 All results to be obtained before baseline visit.
- 2 No more than 6 days before or 6 days after the date scheduled based on the time from baseline visit not from the previous visit.

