6.2 Data handling

Missing data can have an impact upon the interpretation of the trial data. In general, values for missing data will not be imputed unless otherwise specified. For baseline value, if it is missing at baseline visit, then the latest non-missing value of screening will be used to replace.

All serum HBV DNA results below the lower limit of detection (<20 IU/mL) or results of “not detected” will be analyzed as being the value of the lower limit of quantification, which is 20 IU/mL. For patients whose week 240 visits were influenced by COVID-19, a safety follow-up were added for these subjects. The missing week 240 will be imputed from safety follow-up visit in the analysis of primary endpoints. Please refer to section 7.4 for details.

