Figure	4.5.1	The Proportion (95% CI) of Subjects with HBV DNA <20 IU/mL Over Time - mITT
Figure	4.5.1.1	The Proportion (95% CI) of Subjects with HBV DNA <69 IU/mL Over Time - mITT
Figure	4.8.1.1	Mean HBV DNA Log10 IU/mL Over Time by Baseline ALT Significance - mITT
Figure	4.8.3	Distribution of HBV DNA levels Over Time - mITT
Figure	4.15.1	Kaplan-Meier Curves for Newly Diagnosed Hepatocellular Carcinoma (HCC) – mITT
Figure	4.15.1.1.1	Kaplan-Meier Curves for Newly Diagnosed Hepatocellular Carcinoma (HCC) in Subjects with Platelets <100 - mITT
Figure	4.15.1.1.2	Kaplan-Meier Curves for Newly Diagnosed Hepatocellular Carcinoma (HCC) in Subjects with Platelets >=100 - mITT
Figure	4.15.3	Kaplan-Meier Curves for Disease Progression – mITT
Figure	4.15.3.1.1	Kaplan-Meier Curves for Disease Progression in Subjects with Platelets <100 - mITT
Figure	4.15.3.1.2	Kaplan-Meier Curves for Disease Progression in Subjects with Platelets >=100 - mITT
Figure	4.18.3.1	Decline in LSM from baseline to Week 240 - mITT
Figure	5.3.1.1	Mean Estimated Glomerular Filtration Rate Over Time by Baseline eGFR - SA
Figure	5.3.1.2	Mean Creatinine Clearance Rate Over Time by Baseline Ccr - SA
Figure	5.3.2	Mean Serum Phosphorus Over Time - SA
Figure	6.1.1	Change of Average LSM/ALT By Visit - mITT
Figure	6.1.2	Change of Average LSM By Visit - mITT
Figure	6.1.3	Change of Median of LSM By Visit - mITT

GlaxoSmithKline (China) Investment Co., Ltd.
Protocol 201213

Version: 2.0
Feb 26, 2021

Figure	6.3.1	Change of Average GPR APRI FIB-4 By Visit - mITT
Figure	6.3.2	Change of Median of GPR APRI FIB-4 By Visit - mITT
Figure	6.4.1	Change of Fibrosis Stage By Visit - mITT

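### The two renal line plots group subjects by the same baseline reading that starts each curve, so change from Day 0 in the low-function group is biased toward reassurance (minor)

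*SAP*

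**What the plan says.** SAP 7.5.3 plans a line plot of "Mean estimated glomerular filtration rate (eGFR) over time by baseline eGFR" and a matching one for Ccr: "clearance rate (Ccr) over time by baseline Ccr, mean serum phosphorus over time will be analyzed by line plots, respectively". SAP 9 lists them for the safety population as Figure 5.3.1.1, "Mean Estimated Glomerular Filtration Rate Over Time by Baseline eGFR - SA", and Figure 5.3.1.2, "Mean Creatinine Clearance Rate Over Time by Baseline Ccr". SAP 5.3 places them among the exploratory endpoints. No cut-points are given.

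SAP 6.1 fixes the grouping value: "Baseline is defined as the last assessment before administration of the study drug". That is normally the Day 0 reading. If it is missing, SAP 6.2 says "the latest non-missing value of screening will be used to replace".

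A second pre-dose reading exists. Protocol Table 1 ticks the row "Chemistry(Liver & Renal function, electrolyte(phosphate and calcium inclusive" at both Screening and Baseline, and its first footnote says of screening: "All results to be obtained before baseline visit". Protocol 5.2 describes an open-label study with one arm.

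**The concern.** A single eGFR or Ccr value is the subject's true level plus visit-to-visit error. Subjects fall below a cut partly because their true level is low and partly because the reading happened to be low. The chance part does not recur, so the low stratum's mean rises at the next visit with no real change, and the high stratum's mean falls. A control arm would show the same artefact and allow it to be subtracted. This study has none.

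The direction matters. The protocol's risk assessment names renal toxicity as a TDF risk, and the low stratum holds the subjects with least renal reserve. A reader will naturally compare later points with the Day 0 point, and in that stratum the comparison is shifted toward apparent stability or gain. No other output listed in SAP 9 shows renal function over time by starting function.

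**Working it through.** **Inputs from the documents.** Baseline is one pre-dose reading (SAP 6.1). Chemistry is taken at screening and at Day 0 (Protocol Table 1). Entry requires Ccr of at least 70 mL/min (Protocol 4.3). There is one arm, with 186 subjects enrolled. The plan states no figure for these plots that could be reproduced. The 186 is used only to turn percentages into counts, and it does reproduce: 0.05 × 0.95 × (1.96/0.034)² = 157.8, so 158; 158/0.85 = 185.9, so 186.

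**Inputs assumed.** Mean 100 mL/min, SD 15, cut at 90 or 80, independent errors between visits, and within-person variability over a range. None of these is in the documents. One generic renal measure stands for both eGFR and Ccr.

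**Step 1: closed form.** With no true change, the expected shift in the group whose Day 0 value X0 is below c is

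(1 − ρ) × (μ − E[X0 given X0 < c]),

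where ρ is the correlation between two visits. Take μ = 100, total SD 15 and c = 90. The standardised cut is −0.667 and about 25% of subjects lie below it. Their mean is 100 − 15 × 1.265 = 81.0, so the distance to the overall mean is 19.0. The shift is:

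- ρ = 0.7: 0.30 × 19.0 = +5.7
- ρ = 0.8: 0.20 × 19.0 = +3.8
- ρ = 0.9: 0.10 × 19.0 = +1.9
- ρ = 0.95: 0.05 × 19.0 = about +0.95

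Simulation with the entry limit applied to the screening value gives +6.1, +4.1 and +2.1 for ρ = 0.7, 0.8 and 0.9.

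**Step 2: simulation by within-person CV.** True values are normal with mean 100 and SD 15. Three readings (screening, Day 0, later) carry independent multiplicative error, and entry requires screening of at least 70. Results in mL/min, cut at 90:

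| Within-person CV | 4% | 6% | 8% |
|---|---|---|---|
| Low stratum, no true change | +1.2 | +2.6 | +4.5 |
| High stratum, no true change | −0.4 | −0.9 | −1.6 |
| Low stratum, true loss of 3 in everyone | −1.8 | −0.4 | +1.5 |
| Low stratum, true loss of 5 in everyone | −3.8 | −2.4 | −0.5 |
| Either stratum formed on screening, change from Day 0, no true change | 0.0 | 0.0 | 0.0 |
| Subjects whose screening and Day 0 strata differ | 9% (17 of 186) | 13% (25) | 18% (33) |

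The two rows with a true loss are the first row minus 3 or minus 5. About 24 to 26% of subjects are in the low stratum. With the cut at 80, the low stratum is only about 14 to 17 of 186 subjects and its lift is +1.7, +3.6 or +6.1.

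**Step 3: when the artefact occurs.** Take ρ = 0.8, cut 90 and a true loss of 1 mL/min per 48 weeks, which is 5 over 240 weeks. The low stratum's mean is 82.0 at Day 0, 85.9 at Week 12 and 81.1 at Week 240.

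- Read from Day 0, the loss looks like 82.0 − 81.1 = 0.9.
- Read from Week 12, it is 85.9 − 81.1 = 4.8, against a true 228/48 = 4.75.

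The bias is one step at the start, and the later slope is right.

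**The case against.** The strongest reply is that little depends on these two plots. They are exploratory and descriptive, with no test or decision attached. Several renal outputs do not use this grouping: chemistry change from baseline by visit (Table 5.3.2), confirmed creatinine rises of at least 0.5 mg/dL, Ccr below 50 mL/min, and Grade 3 or 4 creatinine. Confirmed Ccr of 50 mL/min or less is also a component of the primary disease-progression endpoint. This stands. A reader might infer that the grouping could hide TDF renal toxicity from the trial, and the documents do not support that.

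A reader might also infer that the plots will always show low-function subjects gaining or holding function. The table above does not bear this out. At a CV of 4%, a true loss of 3 still shows as −1.8 and a loss of 5 as −3.8. Reversal needs a small loss and high variability, and a progressive decline after Week 12 stays visible in every case.

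Another tempting step is to judge the artefact against ageing. The CKD-EPI age factor in SAP 8.4 would take about 3.2 mL/min off 100 over 240 weeks if age advanced by visit (0.993 to the power 4.6 is 0.968). But SAP 7.2.1 fixes age from the year of consent, and no rule updates it, so that yardstick is not established.

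It is also true that every size rests on assumed inputs, and that strata formed on screening no longer match baseline as SAP 6.1 defines it. These objections limit the importance of the point. They do not remove the bias in the comparison with Day 0.

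**Conclusion.** The point holds in a limited form and is minor. In Figures 5.3.1.1 and 5.3.1.2 the grouping value is normally also the first plotted point, and the single arm offers no way to subtract regression to the mean. The direction is certain: change from Day 0 is biased upward in the low stratum and downward in the high stratum.

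The size is not known from the documents. Under mean 100, SD 15, cut 90 and a CV of 4 to 8%, the low-stratum lift is about 1.2 to 4.5 mL/min. It falls to about 1 if visits correlate at 0.95. That is enough to distort a small true decline such as 3 mL/min when it is read against Day 0. It does not affect the slope after Week 12, the unstratified renal outputs or the primary endpoint.

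**What to change.** In SAP 7.5.3 and the two figure shells:

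1. Form the eGFR and Ccr strata from the screening value, and state the cut-points.
2. Plot change from the Day 0 value within those strata.
3. Leave out of the stratified change plot any subject with no separate Day 0 reading. For those subjects the SAP 6.2 fallback makes the grouping and reference values the same again.
4. Add the unstratified mean curve to each figure.
5. Relabel the figures as by screening eGFR and by screening Ccr.

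The change is confined to these two figures, because SAP 9 lists no table by baseline renal function. It needs SAP wording and a small programming change, with no new data. The cost is that, under the assumptions above, about 9 to 18% of subjects (roughly 17 to 33 of 186) sit in a stratum that differs from their Day 0 value. Full removal of the artefact also assumes that screening and Day 0 errors are independent. If a short-term fluctuation affects both readings, a remnant would stay.

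Averaging screening and Day 0, for both grouping and reference, is a weaker alternative. At ρ = 0.8 and cut 90 it only roughly halves the artefact, from +4.1 to +1.9.
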